4.3.2.4.3 Onset of Insulin Action

The onset of insulin action is defined as the time in minutes from the beginning of baseline to the first occurrence of a drop in blood glucose concentration by 5 mg/dL from its maximum. It will be based on the actual time.

- If the blood glucose never dropped by 5 mg/dL from time 0, it will be set as missing.

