Secondary Endpoints 1:	
Mean differences (within treatments over time and between treatments at specified time points) in:
 
 Time-to-Maximum Glucose Infusion Rate (GIR) ($t_{max(GIR)}$) Time to half-maximal GIR, both early and late ($t_{50(GIR),early}$ & $t_{50(GIR),late}$) Onset of action as measured by a drop of blood glucose (BG) by 5 mg/dL Duration of insulin action (calculated the same as MRT for PK) GIR_{max} Area under the GIR curve ($AUC_{0-t(GIR)}$), both absolute and as a percentage of total $AUC_{0-\infty}$ and Coefficient of Variation (CV) of $AUC_{0-t(GIR)}$, where $t = 5, 10, 15, 20, 30, 45, 60, 90, 120, 150, 180, 210, 240,$ and 300 min 
Other PD parameters may also be calculated.

Secondary Objective 2:	To assess pharmacokinetic (PK) parameters within and across treatments following subcutaneous delivery using Achilles vs Teflon control set on DOI and days 3, 5, and 7 post insertion.
Secondary Endpoints 2:	
Mean differences (within treatments over time and between treatments at specified time points) in:
 
 • Early exposure ($AUC_{0-60min}$) • Mean-residence time (MRT) of insulin • Maximum Insulin concentration (C_{max}) • Time-to-Maximum Insulin Concentration (t_{max}) • Time-to-50% Maximum Insulin Concentration [$t_{50,early}$ & $t_{50,late}$], both early (i.e. before C_{max}) and late (i.e. after C_{max}) • $AUC_{(0-t)}$ (both absolute and as a percentage of $AUC_{(0-300)}$) and Coefficient of Variability (CV) $AUC_{(0-t)}$ where $t = 3, 6, 9, 12, 15, 20, 25, 30, 35, 40, 45, 50, 60, 70, 80, 90, 105, 120, 150, 180, 210, 240$ and 300 min 
Other PK parameters may also be calculated.

Secondary Objective 3:	To assess continuous glucose monitoring (CGM) data, comparing data within and across treatments.
Secondary Endpoints 3:	
 • Mean daily time in range (70-180 mg/dL), DOI through Day 7 inclusive • Mean daily time in target (70-140 mg/dL), DOI through Day 7 inclusive • Mean and median daily glucose, DOI through Day 7 inclusive • Glucose variability (%CV), DOI through Day 7 inclusive • Mean daily time ≤ 70 mg/dL, < 54 mg/dL, DOI through Day 7 inclusive • Mean daily time > 140 mg/dL, > 180 mg/dL, > 240 mg/dL, DOI through Day 7 inclusive • Other CGM metrics may also be calculated
Secondary Objective 4:	To assess performance of investigational infusion set on DOI through 7 for each treatment

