The run-in period should last no longer than 3.5 hours, if BG is not stable after this time, the participant cannot continue in the study and is sent home. He/she may return another day. Once the BG level of approximately 95 ± 15 mg/dL has been maintained for at least 40 minutes (measured every 10 minutes), the IV insulin (dextrose) is discontinued, and the baseline will be recorded for 20 min (blood draw every 5 min). 20 minutes after discontinuation of IV insulin, a SC bolus of lispro insulin (0.15 U/kg) is administered via the pump (t0). Baseline plasma glucose level is defined as mean plasma glucose at time points t-20, t-15, t-10, t-5, and t0. After t0, blood samples for PK analysis are drawn every 3 minutes for 15 min (Clamp Part I), every 5 minutes for 40 minutes (Clamp Part II), every 10 min for 30 min (Clamp Part III), and every 15 minutes for 45 minutes. In the Final Phase, blood is drawn every half an hour until clamp termination at 300 minutes (see Table 6). Up to 15 blood samples will be obtained overnight prior to the day of the glucose clamp procedure, and 8 additional blood samples will be obtained during stabilization on the morning of the clamp procedure prior to administration of the insulin bolus. Blood samples for immediate glucose determination will be drawn every 5 minutes for 60 minutes following insulin bolus, and then every 10 minutes for the remainder of the clamping period at 300 minutes post-bolus. Blood samples will be acquired using aseptic technique and double stopcock technique to minimize blood loss. A maximum of 66 samples (24 x 1.5 mL [for BG and insulin] + 6 x 1.0 mL [for PK only] + 36 x 0.5 mL for BG only = 62.0 mL) will be drawn during the stabilization period and the clamp procedure, resulting in a total blood loss of 248 mL during 4 clamps over each week. Combining both

clamping weeks, this represents less than 1 unit of blood (=525 mL). Blood samples will be centrifuged to plasma, plasma glucose concentration measured, and plasma frozen in 2 aliquots for future measurement of insulin concentration. The detailed clamp sampling schedule is summarized in Table 6.

Table 6. Clamp visit sampling schedule

Phase	Approximate Clock Time (hh:mm)	Nominal Time (min)	No. of samples	Volume/Sample (mL)	Total Volume (mL)
Stabilization, over night			15	0.5	7.5
Baseline Part I	7:00	-60	5	0.5	2.5
	7:10	-50		0.5	
	7:20	-40		0.5	
	7:30	-30		0.5	
	7:40	-20		0.5	
Discontinue IV insulin & Dextrose					

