Baseline Part II	7:45	-15	3	1.5	4.5
	7:50	-10		1.5	
	7:55	-5		1.5	
Bolus	8:00	0	1	1.5	1.5
Clamp Part I	8:03	3	7	1	6.5
	8:05	5		0.5	
	8:06	6		1	
	8:09	9		1	
	8:10	10		0.5	
	8:12	12		1	
	8:15	15		1.5	
Clamp Part II	8:20	20	9	1.5	13.5
	8:25	25		1.5	
	8:30	30		1.5	
	8:35	35		1.5	
	8:40	40		1.5	
	8:45	45		1.5	
	8:50	50		1.5	
	8:55	55		1.5	
	9:00	60		1.5	
Clamp Part III	9:10	70	3	1.5	4.5
	9:20	80		1.5	
	9:30	90		1.5	
Clamp Part IV	9:40	100	10	0.5	8.0
	9:45	105		1	

Phase	Approximate Clock Time (hh:mm)	Nominal Time (min)	No. of samples	Volume/Sample (mL)	Total Volume (mL)
	9:50	110		0.5	
	10:00	120		1.5	
	10:10	130		0.5	
	10:15	135		1	
	10:20	140		0.5	
	10:30	150		1.5	
	10:40	160		0.5	
	10:50	170		0.5	
	11:00	180		1.5	
	11:10	190		0.5	
	11:20	200		0.5	
	11:30	210		1.5	
	11:40	220		0.5	
	11:50	230		0.5	
Final Phase	12:00	240	13	1.5	11.5
	12:10	250		0.5	
	12:20	260		0.5	
	12:30	270		1.5	
	12:40	280		0.5	
	12:50	290		0.5	
	13:00	300		1.5	
Observation at site			66 total samples		
				Total volume per clamp =	62.0 mL

During the 5-hour clamp plasma glucose concentration will be maintained at 95 ± 15 mg/dL with IV infusion of dextrose (0.1 to 4 mg/kg/min), titrated using a computerized dosing algorithm according to frequent BG measurements. The trigger plasma glucose concentration for onset of glucose infusion will be a value that is 5 mg/dL below the mean obtained during Baseline Part II (i.e. -15, -10 and -5 minutes before bolus delivery at T=0). The dosing calculator will be used to determine the optimal glucose infusion rate (GIR) for each subsequent time period between BG measurements. If insulin is infused, glucose infusion must be stopped and vice versa. The dextrose infusion rate will be increased to match insulin lispro's glucose lowering effect over time until the glucose lowering effect of the insulin lispro bolus reaches baseline (i.e. glucose infusion rate of 0) or 5 hours after bolus administration.

In the case of persistent hyperglycemia (BG > 250 mg/dL) over 30 minutes without dextrose infusion, the clamp will be terminated early. A correction bolus will be given via the pump and the BG measured to determine whether BG was lowered by 50 mg/dL within 1 hour. If this is not the case, the CSII catheter is

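### The SAP times onset of insulin action from the start of the clamp baseline, 15 to 60 minutes before the bolus, and lets a pre-bolus glucose fall count as onset

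*SAP*

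**What the plan says.** **SAP.** Section 4.3.2.4.3 defines onset as "time in minutes from the beginning of baseline to the first occurrence of a drop in blood glucose concentration by 5 mg/dL", measured down from the glucose maximum, using actual times. It gives no window for the fall or for the maximum. The bullet beneath it uses another origin: "If the blood glucose never dropped by 5 mg/dL from time 0, it will be set as missing". The neighbouring sections 4.3.2.4.1 (tmax(GIR)) and 4.3.2.4.2 (t50(GIR), early and late) are timed from time 0.

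**Protocol.** The synopsis lists the endpoint as "Onset of action as measured by a drop of blood glucose (BG) by 5 mg/dL", with no time origin and no reference level. Section 6.1.1.5 stops IV insulin and dextrose 20 minutes before the bolus, records a baseline over those 20 minutes and gives the bolus at t0. The same section contains three candidate baselines:

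- the text: "Baseline plasma glucose level is defined as mean plasma glucose at time points t-20, t-15, t-10, t-5, and t0";
- Table 6, "Baseline Part I": samples from -60 to -20 minutes, listed before the row that stops IV insulin and dextrose;
- Table 6, Baseline Part II: samples at -15, -10 and -5 minutes. The threshold for starting dextrose is tied to this one: "a value that is 5 mg/dL below the mean obtained during Baseline Part II".

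**Analysis.** Protocol 9.4.3 names onset time among the pharmacodynamic parameters compared between treatments. SAP 4.4.4.2.3 leaves it out of its list of tested parameters, so it falls under the descriptive summaries of SAP 4.4.4.2.4.

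**The concern.** Onset is meant to describe how quickly the subcutaneous bolus acts through a given set on a given wear day. A clock that starts before the bolus adds time that has nothing to do with the set. A fall that may occur before the bolus can come from sampling noise or from IV insulin still acting after it is switched off.

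The section also contradicts itself. A clamp with a 5 mg/dL fall before the bolus, but none from time 0 onwards, has an onset under the definition and is missing under the bullet. Two programmers working from this text could derive different onset times from the same clamp.

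The reference level is a further ambiguity. If the maximum is taken over the whole profile, a late glucose peak would make onset very late or undefined. If it is a running maximum, ordinary noise in the baseline samples can satisfy the rule.

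**Working it through.** There is no stated figure to reproduce, because this is a variable definition.

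**1. Offset.** Let T be the true time from bolus to the qualifying fall, and b the time from the beginning of baseline to the bolus. If the first qualifying fall comes after t0, the SAP records T + b. An assumed T of 15 minutes gives:

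| Baseline meant | b (min) | Recorded onset (min) |
|---|---|---|
| Table 6, Part II | 15 | 15 + 15 = 30 |
| Protocol text, five points | 20 | 15 + 20 = 35 |
| Table 6, Part I | 60 | 15 + 60 = 75 |

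**2. Effect on contrasts.** Take assumed true onsets of 15 and 20 minutes.

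- Difference: (20 + b) - (15 + b) = 5 minutes for any b. The offset cancels.
- Ratio: 15/20 = 0.75 from the bolus. With b = 15 it is 30/35 = 0.86, with b = 20 it is 35/40 = 0.875, and with b = 60 it is 75/80 = 0.94. A ratio would shrink towards 1, but neither document plans one for onset.

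**3. Pre-bolus falls.** The documents give no glucose noise SD and no drift after IV insulin stops, so both are assumptions. The check simulated 200,000 series per setting at the protocol's sampling times, with independent normal noise. It counted series in which some value lay at least 5 mg/dL below the running maximum by t0.

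| Samples from | Drift after t-20 (mg/dL/min) | SD 1 | SD 2 | SD 3 |
|---|---|---|---|---|
| -15 to 0 | 0 | 0.1% | 17% | 43% |
| -20 to 0 | 0 | 0.2% | 25% | 56% |
| -20 to 0 | -0.1 | 3% | 42% | 68% |
| -60 to 0 | 0 | 0.6% | 53% | 88% |

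Hand check for the second row: one ordered pair of samples differs by at least 5 with probability Φ(-5/(SD·√2)), and five samples give 10 ordered pairs. At SD 1 this is Φ(-3.54) = 0.0002, and 10 × 0.0002 = 0.2%, matching the simulation. At SD 2 it is Φ(-1.77) = 0.038, so the upper bound is 38%. The simulated 25% is lower because the pairs overlap.

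**4. What such clamps record.** With sampling from t-20, a clamp that meets the rule by t0 records at most 20 minutes, on average about 13 to 14. That is the time of a noise or drift event, not T + 20.

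**The case against.** The case for treating this as minor is substantial, and most of it stands.

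- **Use of the endpoint.** The SAP only describes onset. It was revised after the sponsor ended the study at the seventh completer, so what is at stake is a small descriptive summary. Speed of action is also covered by tmax(GIR) and early t50(GIR), which are timed from time 0 and tested, and by the insulin AUC over the first 60 minutes.
- **A biased set comparison.** A reader might infer one from the offset. The synopsis frames the secondary endpoints as mean differences, and a fixed shift cancels there.
- **A uniform overstatement.** A reader might infer that every onset is too long by the same amount. That cannot hold alongside pre-bolus triggers, whose recorded times can be short, so the error has no single direction.
- **Run-in and residual IV insulin always counted.** This too might be inferred. On the t-20 reading, the clock starts after the stability period of at least 40 minutes. Residual IV insulin matters only if it produces the 5 mg/dL fall.
- **Frequency.** The percentages run from negligible to most clamps and rest wholly on assumed noise, independence and a running maximum. The protocol names a reference analyser and requires prior stability, both of which favour the low end.
- **Loose drafting.** The bullet's use of time 0, and the SAP's use of the time-0 value for its baseline-adjusted AUCs, suggest that a time-0 origin may have been intended.

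None of this rescues the definition. It names an origin that precedes the bolus on every reading, and loose drafting is a reason to correct it. Descriptive means are also where an error of 15 to 60 minutes shows directly.

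**Conclusion.** The definition is wrong as written and should be corrected; the consequence is limited. For clamps whose first qualifying fall follows the bolus, onset is overstated by 15, 20 or 60 minutes, according to the baseline meant. This follows from the protocol's timeline and needs no assumption. Additive contrasts among such clamps are unaffected, but the reported values are wrong.

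Clamps with a pre-bolus fall carry no information on the set, and that does not cancel. Their share cannot be known from the documents: about 0.2% to 56% from t-20, assuming independent noise of SD 1 to 3 mg/dL, no drift and a running maximum. That range shows the rule permits the error. It does not show that the error is common.

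The primary endpoint is untouched. The documents do not support reading this as a flaw in the trial's main comparison.

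**What to change.** Redefine onset in SAP 4.3.2.4.3 as the minutes from actual bolus time (t0) to the first post-bolus glucose at least 5 mg/dL below a stated pre-bolus baseline mean. Set it missing only if no post-bolus value qualifies, and reword the bullet to match.

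State which mean applies. Protocol 6.1.1.5 defines baseline glucose over five points (-20 to 0 minutes) but ties the dextrose threshold to the three Baseline Part II points. The SAP must reconcile the two for this parameter. Using the Part II mean would align onset with the reference the clamp already uses; the clamp procedure itself need not change.

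The new rule is better but not free of noise. With no insulin effect, independent noise and the Part II mean, it would fire falsely by 15 minutes in about 4% of clamps at SD 2 and 19% at SD 3.

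The cost is a sentence or two in the SAP and a short programming change. The glucose samples involved are already in the protocol's schedule. If onset has already been tabulated, it can be re-derived from the stored values.

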4.3.2.4.4 Duration of Insulin Action

Duration of insulin action is calculated similar to Mean Residence Time (MRT). It is calculated as:

$$\text{Duration of insulin action} = \frac{AUMC_{0-300}}{AUC_{0-300}}$$

AUMC is the area under curve of $GIR_t * t$, and is estimated using the same method as described for AUC in section 4.3.2.1.

4.3.2.4.5 Percentage of AUC_{0-300} and Coefficient of Variability (CV) AUC

$$\text{Percentage of } AUC_{0-300} = 100 \times \frac{AUC_{0-t}}{AUC_{0-300}}$$

CV of AUC is calculated per week for each subject and,

$$CV = \frac{\text{Standard Deviation of AUC each week}}{\text{Mean of AUC each week}}$$

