2.5 MODIFICATIONS FROM THE STATISTICAL SECTION IN THE PROTOCOL

After the 7th subject completed the study, sponsor decided to terminate the study.
Thus :

- The analyses carries out using all available data will be considered as final analyses. No intrime analyses will be carried out.
- All analyses defined in this SAP will be done. However, it is expected some of them may not have results/outputs generated due to the small sample size.

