4.3.2.3.2 Terminal Rate Constant λ

Terminal rate constant λ is needed before we estimate AUC_{0-t} . It is estimated by:

- a. Find the GIRs after GIR_{max} (section 4.3.2.3.1)
 - i. If there only 1 or 0 available GIR reading after GIR_{max} , then λ will be set as missing.
- b. Do a regression of log-transformed GIR vs Time
- c. λ is the slope from this regression
- d. In a “No Peak” case, λ will be set as missing

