4.3.2.3.3 AUC_{0-t}

The AUC_{0-t} of GIR over wear time will be calculated using trapezoid rule and the actual time points. Missing data for the calculation of the AUC will be handled as followed:

1. If the reading for Time 0 is missing, it will be the average of up to 3 prior readings. However, if there is no prior readings available, it will be assumed to be 0
2. If the reading at (actual) time t ($t < 300$ min) is missing, it will be imputed with linear interpolation
3. If the reading at $t=300$ min is missing:
 - a. The reading at $t=300$ min will be imputed using the regression line obtained when estimate λ (section 4.3.2.3.1).
 - b. If λ is missing, AUC_{0-t} will be set as missing.

4.3.2.3.4 $AUC_{0-\infty}$

$AUC_{0-\infty}$ is estimated as

$$AUC_{0-\infty} = AUC_{0-last} + AUC_{last}, \text{ where } AUC_{last} = GIR_{last}/\lambda$$

If λ is missing, then $AUC_{0-\infty}$ is set as missing.

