4.3.2.5.4 Percentage of AUC_{0-300} and Coefficient of Variability (CV) AUC

These parameters will be calculated with the same methods as described in section 4.3.2.4.5

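### The SAP computes the partial GIR AUC percentage against AUC0-300 where the protocol specifies AUC0-infinity, and does not declare the change

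*SAP*

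**What the plan says.** Protocol 1.1 (Synopsis), Secondary Endpoints 1, asks for AUC0-t of GIR at times from 5 to 300 min, "both absolute and as a percentage of total" AUC0-infinity. Secondary Endpoints 2, the PK list, asks for the corresponding insulin percentage against AUC0-300. The protocol thus names a different denominator for each.

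The SAP has one formula for both. Section 4.3.2.4.5, "Percentage of AUC_{0-300} and Coefficient of Variability (CV) AUC", is a subsection of Other GIR Parameters and gives 100 x AUC0-t/AUC0-300. Section 4.3.2.5.4 reuses it for insulin: "These parameters will be calculated with the same methods as described in section 4.3.2.4.5". That matches the protocol for PK but not for PD.

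SAP 4.3.2.3.4 does derive AUC0-infinity for GIR, as the area to the last reading plus GIR_last/lambda, but no percentage uses it. SAP 2.5, the list of modifications from the protocol, covers early termination, the dropped interim analysis and outputs that may not be produced. It adds "All analyses defined in this SAP will be done" and does not mention a changed denominator.

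**The concern.** As the SAP stands, the PD percentage that the protocol names has no formula, and a different quantity would be reported in its place without notice.

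The two quantities differ whenever glucose is still being infused when observation stops. The design allows this: under protocol 6.1.1.5 the infusion continues until GIR returns to 0 or until 5 hours, and SAP 4.3.2.1 provides for curves still rising at 300 min. Dividing by the area inside the window then removes the late area from the denominator. The 300-min value becomes a constant, and comparison of the two sets at earlier times depends on how much area each has after 300 min.

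**Working it through.** The plan states no figure for this endpoint, so there is nothing to reproduce. The check is algebra followed by an illustration.

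**Algebra.** Let f be the share of AUC0-infinity lying after 300 min, so AUC0-300 = (1 - f) x AUC0-infinity. Then

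SAP % = 100 x AUC0-t/AUC0-300 = protocol %/(1 - f).

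- At t = 300 the SAP value is 100 for every clamp; the protocol value is 100 x (1 - f).
- At earlier t the inflation factor 1/(1 - f) is 1.00 at f = 0, 1.05 at 5%, 1.11 at 10%, 1.25 at 20% and 1.43 at 30%. The 0% to 30% range for f is an assumption.
- The slow/fast ratio of percentages is multiplied by (1 - f_fast)/(1 - f_slow). This exceeds 1 only if the slower set has the larger tail.

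**Illustration (assumed curves).** Take gamma-shaped GIR curves with x = t/theta. For shape 2, theta = peak time and F(t) = 1 - exp(-x)(1 + x). For shape 3, theta = peak/2 and F(t) = 1 - exp(-x)(1 + x + x²/2). The protocol percentage is 100 F(t) and the SAP percentage is 100 F(t)/F(300). For shape 3 with a 120-min peak, theta = 60:

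- F(300) = 1 - exp(-5) x 18.5 = 0.875, so f = 12.5%.
- F(120) = 1 - exp(-2) x 5 = 0.323, so the protocol gives 32.3% and the SAP 32.3/0.875 = 36.9%.

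Between-set differences in percentage points, protocol to SAP:

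| Shape; peaks (min) | f fast, f slow | At 120 min | At 240 min |
|---|---|---|---|
| 3; 45 vs 60 | 0.0%, 0.3% | 13.9 to 13.7 (1% lost) | 1.2 to 1.0 (21% lost) |
| 3; 60 vs 90 | 0.3%, 3.8% | 26.4 to 24.6 (7% lost) | 8.5 to 5.3 (38% lost) |
| 3; 90 vs 120 | 3.8%, 12.5% | 17.5 to 14.9 (15% lost) | 13.9 to 6.6 (52% lost) |
| 2; 60 vs 90 | 4.0%, 15.5% | 20.9 to 16.4 (22% lost) | 16.3 to 6.5 (60% lost) |

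These are examples, not bounds. A heavier-tailed pair (shape 2, peaks 90 vs 120, tails 15.5% and 28.7%) goes from 12.1 to 8.5 points at 120 min (30% lost) and from 15.1 to 4.8 at 240 min (68% lost).

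**Tails ordered the other way.** Compare shape 2 peaking at 75 min (f = 9.2%) with shape 3 peaking at 90 min (f = 3.8%). At 60 min the difference grows from 4.1 points (19.1 vs 15.1) to 5.4 (21.0 vs 15.7). At 120 min it changes sign: 47.5 vs 49.8 becomes 52.3 vs 51.8.

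**Would the SAP's own AUC0-infinity serve?** Not as written. SAP 4.3.2.3.2 states that "λ is the slope from this regression", meaning log GIR on time after the peak. On a falling curve that slope is negative, so GIR_last/lambda subtracts area. In the shape 3 curves on the clamp sampling grid, the literal AUC0-infinity/AUC0-300 is 0.944 (peak 90) and 0.771 (peak 120), which puts the 300-min percentage at 100/0.944 = 106 and 100/0.771 = 130. With lambda as minus the slope the ratios are 1.056 and 1.229, against true values of 1.040 and 1.142. The sign is then right, but the tail is overstated in these curves.

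**The case against.** The strongest reply is that the mismatch is a matter of documentation and its effect is unproven. If GIR is back to 0 by 300 min, f = 0 and the denominators agree, and the documents give no profile to say otherwise. That stands, and it limits what can be said about size.

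A reader might infer that the SAP formula makes a slower set look faster, or always biases the comparison toward no difference. The documents do not support this. It needs GIR above 0 at 300 min and a larger tail for the slower set, and the mixed-shape example shows the difference growing.

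A reader might also infer that the trial loses its measure of delayed action. It does not: time to maximum GIR, early and late t50, onset and duration remain, and absolute AUC0-t is unchanged. SAP 4.4.4.2.3 names tmax, t50 and duration for treatment testing. The percentage is not named there and is descriptive only, unless it falls under the AUCs.

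The protocol's denominator has its own weakness. AUC0-infinity is missing for no-peak curves (SAP 4.3.2.1), which may be the slowest profiles, while AUC0-300 keeps them. This stands and is why both versions should be shown.

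Finally, the study stopped after the 7th subject and some outputs may not appear. That lowers the practical weight but does not remove the undeclared departure.

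**Conclusion.** The departure is certain: for GIR, the SAP does not compute the percentage the protocol defines, and SAP 2.5 does not say so. Two consequences are also certain: 100% for every clamp at 300 min, and inflation by 1/(1 - f) at earlier times whenever f is above 0. The direction of the effect on the between-set comparison is conditional on which set has the larger tail. Its size rests wholly on assumed curves: about 1% to 22% of the difference at 120 min and up to about 60% at 240 min in the four tabulated same-shape pairs, more with heavier tails, and none if GIR has returned to 0.

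The primary endpoint, ln(AUC0-300) of GIR, does not use this ratio. Nor do absolute AUC0-t or the other timing endpoints, and the insulin percentage already follows the protocol. Severity is minor: one secondary endpoint.

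**What to change.** In SAP 4.3.2.4.5, compute 100 x AUC0-t/AUC0-infinity for GIR, and keep AUC0-300 for insulin. For the result to be usable:

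- In 4.3.2.3.2, define lambda as minus the regression slope, so that the tail is a positive area.
- Exclude zero GIR values from the log regression, and state that the tail is zero when the last GIR is 0.
- Report the extrapolated share for each clamp.
- Report 100 x AUC0-t/AUC0-300 beside it, with the number of clamps in which AUC0-infinity is missing, by set and day.

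Alternatively, keep AUC0-300 for GIR, list it in SAP 2.5 as a changed endpoint with the reason, and drop the 300-min value.

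The cost of the first route is a revised formula, a corrected lambda definition and a few extra columns; no new data are needed. Its downside is that the AUC0-infinity percentage is missing or noisier where the tail cannot be extrapolated well. The second route costs a few lines of text but gives up the protocol's definition.
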